7.7.3 Electrocardiograms

The 12-lead ECG will be measured at screening (Visit 1), Week 12 (Visit 5) and Week 24 (Visit 8) including heart rate (beats/min), PR interval (msec), QRS interval (msec), QT interval (msec), QTc interval (msec) and investigator interpretation of ECG. Fridericia corrected QT (QTcF) interval (msec) will be calculated as $(QT/(60/HR))^{1/3}$.

The quantitative ECG data will be summarised using standard descriptive statistics on actual values and change from baseline at each scheduled visit and final visit for the Safety subjects.

Shift tables of investigator assessment of ECG (normal, abnormal not clinically significant, abnormal clinically significant) from baseline to each scheduled post-baseline visit and final visit will be presented by treatment group and overall.

Potentially Clinically Significant Abnormalities (PCSA) for ECG

Any case with none sinus rhythm is considered to be PCSA. The PCSA criteria in subjects with sinus rhythm are listed in the table below. The number and percentage of subjects with PCSA for each below parameter will be summarised by treatment group and overall at each scheduled visit, final visit and any post-baseline visit. The number and percentage of subjects with abnormal PCSA values (PCSA-low and PCSA-high) at any post-baseline will be summarised by different baseline values (normal, abnormal) and parameters

Table 3 PCSA Criteria for ECG

ECG test Name	PCSA – Sinus Rhythm (Y/N)*	PCSA – Low Criteria	PCSA – High Criteria	PCSA – Chang from baseline	Normal range	Unit
Heart Rate (collected from CRF)	Y	< 50	≥ 120	NA	60-100	bpm
PR Interval (collected from CRF)	Y	< 120	≥ 240	NA	120-200	ms
QRS Interval (collected from CRF)	Y	NA	≥ 120	NA	60-100	ms
QT interval (collected from CRF)	Y	NA	NA	NA	320-440	ms
QT Interval, Corrected (collected from CRF)	Y	≤300	≥ 470	≥ + 45	>300 and <440	ms
QTcF (calculated by programming)	Y	≤300	≥ 470	≥ + 45	>300 and <440	ms

*Y/N= yes/no; Y = sinus rhythm.

Statistical Analysis Plan

Version: Final 3.1

Ipsen Pharma; Protocol No. D-CN-52014-220

Date of Issue: 13DEC2019

CCI

All ECG data collected during the study will be presented in subject listings. If a subject has at least one ECG measurement meeting PCSA criteria, all her data for that ECG parameter will be presented in a separate listing with flag indicating PCSA-low or PCSA high.

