8.6 Electrocardiography

An ECG analysis will be included as a safety evaluation/endpoint in this study.

The computerised 12-lead ECGs will be recorded at screening (Visit 1), Week 12 (Visit 5) and Week 24 (Visit 8).

Specific machine details will be provided in the Study Manual. Sinus rhythm, heart rate, PR interval, QRS interval, QT interval/corrected QT interval (QTc) will be recorded, as well as clinical significance. A paper copy of each ECG trace will be printed; these copies must be signed by the investigator and identified with subject screening number, initials, date of assessment and study visit. The ECG will be recorded with the subject in supine position after five minutes of rest until four regular consecutive complexes are available.

All ECGs will be evaluated by qualified persons at the study site, and any clinically significant abnormalities observed during the study will be recorded as AEs.

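### The SAP's printed QTcF formula takes the cube root of the whole ratio, so it returns about 7 to 9 instead of a value in milliseconds

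*SAP*

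**What the plan says.** SAP 7.7.3 lists the ECG variables as "heart rate (beats/min), PR interval (msec), QRS interval (msec), QT interval (msec), QTc interval (msec" and adds one derived variable: "Fridericia corrected QT (QTcF) interval (msec) will be calculated as $(QT/(60/HR))^{1/3". Table 3 in the same section has a row for it, "QTcF (calculated by programming", in ms: low at 300 or below, high at 470 or above, change of +45 or more, and normal above 300 and below 440.

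A separate row, "QT Interval, Corrected (collected from CRF", carries identical limits. Protocol 8.6 says of that measurement only that "QT interval/corrected QT interval (QTc) will be recorded, as well as clinical significance". Neither document states which correction lies behind it.

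The derived QTcF enters three kinds of output: descriptive statistics on actual values and changes from baseline, counts of potentially clinically significant abnormalities (PCSA) by visit, and a PCSA listing. The any-post-baseline PCSA counts "will be summarised by different baseline values (normal, abnormal) and parameters". No other place in the protocol or SAP gives a different QTcF formula.

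**The concern.** Fridericia's method divides QT by the cube root of RR in seconds. The printed expression instead divides QT by RR and takes the cube root of the result. The contradiction can be seen without any outside source: the cube root of a quantity in milliseconds is not in milliseconds, and the values cannot lie near the 300 to 470 ms limits set for the same variable.

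Table 3 marks QTcF as a programmed variable, so this line is the programming specification. Following it exactly would make the QTcF outputs meaningless, including the criteria meant to detect prolongation. The derived QTcF is also not a mere duplicate of the collected QTc, because it is the only corrected QT in the documents with a named correction method.

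**Working it through.** **Inputs, all from SAP 7.7.3**

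- Units: QT in msec and heart rate (HR) in beats/min, so 60/HR is RR in seconds.
- QT normal range, from Table 3: "QT interval (collected from CRF) Y NA NA NA 320-440 ms".
- HR normal range, from Table 3: "Heart Rate (collected from CRF) Y < 50 ≥ 120 NA 60-100 bpm".
- QTcF limits: low ≤300, high ≥470, change ≥+45, normal >300 and <440 ms.

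**Formulas**

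- As printed: (QT/(60/HR))^(1/3) = (QT × HR/60)^(1/3)
- Fridericia: QT/(60/HR)^(1/3)

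**Step 1. Can the printed rule reproduce the Table 3 scale?**

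| QT (ms) | HR (bpm) | 60/HR (s) | QT/(60/HR) | As printed | Fridericia (ms) |
|---|---|---|---|---|---|
| 320 | 60 | 1.000 | 320.0 | 6.84 | 320.0 |
| 320 | 100 | 0.600 | 533.3 | 8.11 | 379.4 |
| 400 | 60 | 1.000 | 400.0 | 7.37 | 400.0 |
| 400 | 75 | 0.800 | 500.0 | 7.94 | 430.9 |
| 420 | 90 | 0.667 | 630.0 | 8.57 | 480.8 |
| 440 | 60 | 1.000 | 440.0 | 7.61 | 440.0 |
| 440 | 100 | 0.600 | 733.3 | 9.02 | 521.7 |

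Over the full normal ranges the printed rule spans 6.84 to 9.02 and Fridericia spans 320.0 to 521.7 ms. Only the latter is on the scale of Table 3. The 521.7 is a corner case that pairs the longest normal QT with the fastest normal rate.

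**Step 2. Could any real ECG reach the limits under the printed rule?** To exceed 300 at HR 60, QT would have to exceed 300³ = 27,000,000 ms. To reach 470 it would have to be 470³ = 103,823,000 ms. So every sinus-rhythm value is PCSA-low, none is PCSA-high, and no baseline is in the normal range.

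**Step 3. Could the change criterion be met?** Take a deliberately wide assumed range, QT 200-700 ms and HR 40-150 bpm.

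- Lowest value: (200 × 40/60)^(1/3) = 133.3^(1/3) = 5.11.
- Highest value: (700 × 150/60)^(1/3) = 1750^(1/3) = 12.05.
- Largest possible difference: 6.94, against a criterion of +45.

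A rise in QT from 400 to 450 ms at HR 60 is a true +50 ms. Under the printed rule it is 450^(1/3) − 400^(1/3) = 7.66 − 7.37, or about +0.30.

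**Step 4. Does another reading rescue the formula?** QT in seconds, or RR in milliseconds, gives 0.4^(1/3) = 0.74 at QT 400 and HR 60. Reading the exponent as a power of 1 followed by division by 3 gives 500/3 = 166.7 at QT 400 and HR 75. None of these fits Table 3.

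**The case against.** The strongest objection is provenance. The point turns on the position of one bracket in a formula converted from PDF, and the conversion is imperfect elsewhere in the SAP. If the exponent belongs to the inner bracket on the original page, there is no error. The converted brackets do balance, however, and read coherently as printed. This reservation stands, and it is why the page must be checked first.

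Second, the harm depends on literal programming. The sentence names Fridericia and the unit, Table 3 shows the expected scale, and a value near 7 ms would be hard to miss. The SAP version history also records that Final 3.0 was revised after a dry run and that Table 3 was among the updates. That makes an undetected literal implementation less likely. It does not show that QTcF was derived in that run, or derived correctly. A silent correction by the programmer would also leave the delivered tables at odds with the final SAP.

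Third, the reach is small. The collected QTc is screened against the same limits, so the QT 420/HR 90 case can still be flagged there. The investigator shift tables remain, and clinically significant ECG findings are recorded as adverse events under protocol 8.6. Raw QT and HR are collected, so QTcF can be recomputed at any time. All of this stands. It limits the consequence but does not make the formula correct.

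Finally, the Table 3 criteria apply to sinus rhythm only, and any other rhythm counts as PCSA regardless. The statement that every value would be PCSA-low is therefore confined to sinus-rhythm ECGs.

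**Conclusion.** The concern holds. As printed, the rule yields 6.84 to 9.02 over the SAP's own normal ranges, where Fridericia yields 320 to 522 ms. It contradicts its stated unit and all of the Table 3 limits for QTcF. If implemented literally:

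- the QTcF descriptive statistics, PCSA counts and PCSA listing would be unusable;
- the normal-baseline row of the PCSA-by-baseline table would be empty for QTcF;
- the ≥470 ms and ≥+45 ms criteria could never be triggered in that row.

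The conclusion rests on two conditions: that the original page shows the bracket where the converted text does, and that the formula is programmed as written. A misplaced bracket is the likely origin. The correction should be made before the tables are run, but the matter is limited to one derived safety variable and does not bear on the primary analysis.

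**What to change.** Check the bracket on the original SAP page. If it is as printed, state in SAP 7.7.3: QTcF (ms) = QT (ms)/(60/HR)^(1/3), with HR in beats/min so that 60/HR is RR in seconds.

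Before the tables are run, compare the programmed QTcF values with the Table 3 normal range and, subject by subject, with the QTc collected on the CRF.

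The cost is a one-line SAP correction and a programming check. Data collection does not change.

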7.7.4 Vital Signs

The vital signs will be measured at each visit during treatment and the end of study visit, including systolic blood pressure (mmHg), diastolic blood pressure (mmHg) and heart rate (beats/min).

Descriptive statistics on actual values and change from baseline will be summarised by treatment group and overall at each scheduled visit and the final visit for the Safety subjects.

Potentially Clinically Significant Abnormalities (PCSA) for Vital Signs

The PCSA criteria for selected vital signs in this study are listed in the table below. The number and percentage of subjects with PCSA for each below parameter will be summarised by treatment group and overall at each scheduled visit, final visit and any post-baseline visit. The number and percentage of subjects with abnormal PCSA values (PCSA-low and PCSA-high) at any post-baseline will be summarised by different baseline values (normal, abnormal) and parameters.

Table 4 PCSA Criteria for Vital signs

Parameter	PCSA – Low Criteria	PCSA – High Criteria	Unit
Heart rate	≤50	≥120	bpm
Systolic blood pressure	≤80	≥160	mmHg
Diastolic blood pressure	≤50	≥100	mmHg

The normal ranges for vital signs are defined as below:

- Heart rate: 60-100 bpm
- Systolic blood pressure: 90-139 mmHg
- Diastolic blood pressure: 60-89mmHg

Note: the number is inclusive.

All vital signs data collected during the study will be presented in subject listings. If a subject has at least one vital sign measurement meeting PCSA criteria, all her data for that vital sign parameter will be presented in a separate listing with flag indicating PCSA-low or PCSA high.

7.7.5 Physical/Pelvic Examination

The physical/pelvic examination will be performed at screening (Visit 1), Week 12 (Visit 5) and Week 24 (Visit 8).

Shift tables of test results (normal, abnormal not clinically significant, abnormal clinically significant) from baseline to each scheduled post-baseline visit and final visit will be presented by treatment group and overall.

All physical/pelvic examination data collected during the study will be presented in subject listings.

Statistical Analysis Plan

Version: Final 3.1

Ipsen Pharma; Protocol No. D-CN-52014-220

Date of Issue: 13DEC2019

CCI

7.7.6 Pelvic type B ultrasound

The pelvic type B ultrasound scan will be performed at screening (Visit 1), Week 12 (Visit 5, optional based on investigator judgment) and Week 24 (Visit 8).

Shift tables of test results (normal, abnormal not clinically significant, abnormal clinically significant) from baseline to each scheduled post-baseline visit and final visit will be presented by each treatment group and overall.

All pelvic type B ultrasound scan data collected during the study will be presented in subject listings.

7.7.7 Hormones

Serum E2, FSH and LH concentrations at Week 40 will be listed separately for those subjects with menses not recovered before Week 40.

7.8 Pharmacokinetics

The individual plasma triptorelin concentration is measured in all subjects receiving study drug at Day 1 (Visit 2), Week 4 (Visit3), Week 8 (Visit 4), Week 12 (Visit 5) and Week 24 (Visit 8). Additional sampling is performed for subjects within the PK/PD subgroup.

- The individual plasma triptorelin concentration will be summarised using descriptive statistics (n, mean, SD, %CV, geometric mean, geometric CV, median, minimum and maximum) by treatment group at each scheduled visit for the Sparse PK Sampling set.
- The individual plasma triptorelin concentrations for the Full PK Profile Analysis set will be summarised using descriptive statistics (n, mean, SD, %CV, geometric mean, geometric CV, median, minimum and maximum) by time-point (described as hours/days post-dose), for each treatment group, following each administration.
- To compute descriptive statistics, all BLQ values must be replaced by missing/zero in the data set according to the rules set in [section 6.2.1](#). BLQ values substituted by 0 are included in the calculation of descriptive statistics whereas missing values are ignored. The descriptive statistics should be displayed by visit/time point, and by treatment group only if at least 2/3 (2 out of every 3 values) of the data are available and above the limit of quantification. Otherwise, only minimum and maximum are reported. Individual and mean plasma concentration time profiles, as well as spaghetti plots, on the Full PK Profile Analysis Set will be generated separately based on a dedicated PK analysis plan.

7.9 Interim Analysis

No interim analyses will be performed.

8 CHANGES IN PLANNED ANALYSES

Not applicable.

10 APPENDICES

Appendix I - Schedule of Events

Table 5 Study Procedures and Assessments (All Subjects)

	Screening period	Treatment period										Follow up period [a]			
		Visit 1	Visit 2	Visit 3	Visit 4	Visit 5	Visit 6	Visit 7	Visit 8	Visit 9	Visit 10	Visit 11	End of study/early withdrawal visit		
Procedures and assessments	Screening up to -5 weeks	Baseline (1 st to 5 th day of menses)	Week 4	Week 8	Week 12	Week 16	Week 20	Week 24	Week 28	Week 32	Week 36	within 15 days after menses recovery or Week 40[b]			
Visit window (days)	-35 to -1	Day 1	Day 29 ±3	Day 57 ±3	Day 85 ±3	Day 113 ±3	Day 141 ±3	Day 169 ±3	Day 197 ±3	Day 225 ±3	Day 253 ±3	Day 281 ±3			
Informed consent	X														
Demography	X														
Significant medical or surgical history	X														
Prior medications for endometriosis	X														
Inclusion and exclusion criteria	X	X													
E2, FSH and LH		X[c]	X[c]	X[c]	X[c]									X[d]	
VAS		X	X	X	X		X	X						X	
Physical examination[e]	X				X			X							
Pelvic examination	X				X			X							
Vital signs	X	X	X	X	X	X	X	X						X	

Statistical Analysis Plan

Table 6 Full PK/PD Assessments day 1 to Week 12 (PK/PD Subgroup Subjects)

Assessment[a]	Treatment period											
	Day 1	Week 1 (hours post Day 1 dosing)		Week 2 Day 15	Week 3 Day 22	Week 4 Day 29	Week 6 Day 43	Week 8 Day 57	Week 10 Day 71	Week 12 Day 85		
Assessment time (study day/hours postdose)[b]	Day 1	24	48	168								
PK (3M)	X[c]	X	X	X	X	X	X	X		X[c]		
PK (1M)	X[c]	X	X	X	X	X[d]		X[d]	X	X[d]		
PD (E2, FSH and LH)				X	X							
AEs	X		X	X	X		X	X	X			
Prior and concomitant medication/therapies	X		X	X	X		X	X	X			

1M=triptorelin acetate PR 1-month; 3M=triptorelin pamoate PR 3-month; AE=adverse event; E2=oestradiol; FSH=follicle stimulating hormone; LH=luteinising hormone; PD=pharmacodynamics; PK=pharmacokinetics.

- a assessments to be conducted with samples from the subjects in the full PK/PD subgroup (comprising up to 16 subjects receiving 3M and up to 16 subjects receiving 1M; to be enrolled at selected sites) only
- b time windows for full PK/PD assessments will be defined in the Study Manual
- c samples taken predose and 0.5, 1, 2, 4, 8 and 12 hours postdose
- d samples taken predose

Statistical Analysis Plan

Version: Final 3.1

Ipsen Pharma; Protocol No. D-CN-52014-220

Date of Issue: 13DEC2019

Covance Study ID: 000000154358/8353190

Table 7 Full PK/PD Assessments Week 13 to End of Study (PK/PD Subgroup Subjects)

Assessment[a]	Treatment period													End of study/ early withdrawal
	Week 12 (hours post Week 12 dosing)	Week 14	Week 15	Week 16	Week 18	Week 20	Week 24	Week 28	Week 32	Week 36				
Assessment time (study day/hours postdose)[b]	24	48	168	Day 99	Day 106	Day 113	Day 127	Day 141	Day 169	Day 197	Day 225	Day 253	See Table 5	
PK (3M)	X	X	X	X	X	X	X	X	X	X	X	X		
PK (1M)									X	X	X	X		
PD (E2, FSH and LH)											X			
AEs		X		X	X	X	X	X	X	X	X	X	X	
Prior and concomitant medication/therapies		X		X	X	X	X	X	X	X	X	X	X	

1M=triptorelin acetate PR 1-month; 3M=triptorelin pamoate PR 3-month; AE=adverse event; E2=oestradiol; FSH=follicle stimulating hormone; LH=luteinising hormone; PD=pharmacodynamics; PK=pharmacokinetics.

a assessments to be conducted with samples from the subjects in the full PK/PD subgroup (comprising up to 16 subjects receiving 3M and up to 16 subjects receiving 1M; to be enrolled at selected sites) only

b time windows for full PK/PD assessments will be defined in the Study Manual
